## 3. Children 13 to 17 years of age:

0	:	$\leq 20$ mm
1	:	$> 20$ mm to $\leq 50$ mm
2	:	$> 50$ mm to $\leq 100$ mm
3	:	$> 100$ mm

The maximum intensity of fever will be scored as follows:

0	:	$< 37.5$ °C
1	:	$\geq 37.5$ °C to $\leq 38.5$ °C
2	:	$> 38.5$ °C to $\leq 39.5$ °C
3	:	$> 39.5$ °C

The Investigator will assess the maximum intensity that occurred over the duration of the event for all unsolicited AEs (including SAEs) recorded during the study. The assessment will be based on the Investigator's clinical judgement.

The intensity should be assigned to one of the following categories:

- |              |   |  |
|--------------|---|--|
| 1 (mild)     | = | An AE which is easily tolerated by the subject, causing minimal discomfort and not interfering with everyday activities.   |
| 2 (moderate) | = | An AE which is sufficiently discomforting to interfere with normal everyday activities.  |
| 3 (severe)   | = | An AE which prevents normal, everyday activities. In a young child, such an AE would, for example, prevent attendance at school/ kindergarten/ a day-care centre and would cause the parent(s)/ LAR(s) to seek medical advice. In an older child, such an AE would, for example, prevent attendance at work/school and would necessitate the administration of corrective therapy. |

An AE that is assessed as Grade 3 (severe) should not be confused with a SAE. Grade 3 is a category used for rating the intensity of an event; and both AEs and SAEs can be assessed as Grade 3. An event is defined as 'serious' when it meets one of the pre-defined outcomes as described in [Section 9.1.2](#).

#### **9.3.3.2.2. Assessment of causality**

The Investigator is obligated to assess the relationship between the study vaccination and the occurrence of each AE/ SAE. The Investigator will use clinical judgement to determine the relationship. Alternative plausible causes, such as natural history of the underlying diseases, concomitant therapy, other risk factors, and the temporal relationship of the event to the investigational vaccine will be considered and investigated.

There may be situations when a SAE has occurred and the Investigator has minimal information to include in the initial report to the CRO (Quintiles). However, it is very important that the Investigator always makes an assessment of causality for every event prior to submission of the electronic AE/ SAE form (eSource) to the CRO (Quintiles). The Investigator may change his/ her opinion of causality in light of follow-up information and update the SAE information accordingly. The causality assessment is one of the criteria used when determining regulatory reporting requirements.

In case of concomitant administration of multiple vaccines, it may not be possible to determine the causal relationship of general AEs to the individual vaccine administered. The Investigator should, therefore, assess whether the AE could be causally related to vaccination rather than to the individual vaccines.

All solicited local (injection site) reactions will be considered causally related to vaccination. Causality of all other AEs should be assessed by the Investigator using the following question:

*Is there a reasonable possibility that the AE may have been caused by the study vaccine?*

- YES : There is a reasonable possibility that the study vaccine contributed to the AE.
- NO : There is no reasonable possibility that the AE is causally related to the administration of the study vaccine. There are other, more likely causes and administration of the study vaccine is not suspected to have contributed to the AE.

If an event meets the criteria to be determined as ‘serious’ (see [Section 9.1.2](#)), additional examinations/tests will be performed by the Investigator in order to determine ALL possible contributing factors for each SAE.

Possible contributing factors include:

- Medical history.
- Other medication.
- Protocol required procedure.
- Other procedure not required by the protocol.
- Lack of efficacy of the vaccine, if applicable.
- Erroneous administration.
- Other cause (specify).

#### **9.3.3.3. Assessment of outcomes**

The Investigator will assess the outcome of all unsolicited AEs (including SAEs) recorded during the study as:

- Recovered/resolved.

- Recovering/resolving.
- Not recovered/not resolved.
- Recovered with sequelae/resolved with sequelae.
- Fatal (SAEs only).

#### **9.3.3.4. Medically attended visits**

For each solicited and unsolicited symptom the subject experiences, the subject/ subject's parent(s)/ LAR(s) will be asked if he/she received medical attention defined as hospitalisation, or an otherwise unscheduled visit to or from medical personnel for any reason, including emergency room visits. This information will be recorded in eSource.

### **9.4. Reporting of serious adverse events, pregnancies, and other events**

#### **9.4.1. Prompt reporting of adverse events of specific interest (*clinical symptoms of thrombocytopenia*), serious adverse events, and pregnancies to the contracted research organisation (Quintiles) (Amended 06 May 2015)**

*Adverse events of specific interest (clinical symptoms of thrombocytopenia) that occur in the time period defined in [Section 9.3.1](#) will be reported promptly to the CRO (Quintiles) within the timeframes described in [Table 21](#), once the Investigator becomes aware of the event.*

*(Amended 06 May 2015.)*

SAEs that occur in the time period defined in [Section 9.3](#) will be reported promptly to the CRO (Quintiles) within the timeframes described in [Table 21](#), once the Investigator determines that the event meets the protocol definition of a SAE.

Pregnancies that occur in the time period defined in [Section 9.3](#) will be reported promptly to the CRO (Quintiles) within the timeframes described in [Table 21](#), once the Investigator becomes aware of the pregnancy.

**Table 21** Timeframes for submitting *adverse events of specific interest (clinical symptoms of thrombocytopenia)*, serious adverse events, and pregnancies to the contracted research organisation (Quintiles) (Amended 06 May 2015)

Type of Event	Initial Reports		Follow-up of Relevant Information on a Previous Report	
	Timeframe	Documents	Timeframe	Documents
AEs of specific interest (clinical symptoms of thrombocytopenia)	24 hours*	electronic AE/ SAE form in eSource	24 hours*	electronic AE/ SAE form in eSource
SAEs	24 hours*, ‡	electronic AE/ SAE form in eSource	24 hours*	electronic AE/ SAE form in eSource
Pregnancies	2 weeks*	electronic pregnancy form in eSource	2 weeks*	electronic pregnancy form in eSource

AE = adverse event; SAE = serious adverse event

\* Timeframe allowed after receipt or awareness of the information.

‡ The Investigator will **always provide an assessment of causality** within 24 hours of submission of the SAE.

**9.4.2. Contact information for reporting *adverse events of specific interest (clinical symptoms of thrombocytopenia)*, serious adverse events, and pregnancies (Amended 06 May 2015)**

Study Contact for Reporting AEs of specific interest , SAEs, and pregnancies
Primary method of reporting is via eSource.
If eSource is not available, please refer to SAE/ Pregnancy back-up reporting instructions in the Investigator binder.
Back-up Study Contact for Reporting AEs of specific interest , SAEs, and pregnancies
24/24 hour and 7/7 day availability:
Quintiles Lifecycle Safety
Email : PPD [REDACTED]
Phone : PPD [REDACTED]
Fax : PPD [REDACTED]

**9.4.3. Reporting of adverse events of specific interest (clinical symptoms of thrombocytopenia) to the contract research organisation (Quintiles) (Amended 06 May 2015)**

Once an Investigator becomes aware that an AE of specific interest (clinical symptoms of thrombocytopenia) has occurred in a study subject, the Investigator (or designate) must complete the information in the electronic AE/ SAE form in eSource WITHIN 24 HOURS. The AE and SAE form in eSource is the same form. When an AE of specific interest (clinical symptoms of thrombocytopenia) is indicated on the electronic AE/ SAE form, additional follow-up questions will become available, for completion by the Investigator (or designee). The report will always be completed as thoroughly as

*possible with all available details of the event. Even if the Investigator does not have all information regarding an AE of specific interest (clinical symptoms of thrombocytopenia), the report should still be completed within 24 hours. Once additional relevant information is received, the report should be updated WITHIN 24 HOURS.*

*The Investigator will always provide an assessment of causality at the time of the initial report.*

*Refer to Section 9.4.4.1 for the back-up system in case the electronic reporting system does not work.*

#### **9.4.4. Completion and transmission of serious adverse events reports to the contracted research organisation (Quintiles)**

Once an Investigator becomes aware that a SAE has occurred in a study subject, the Investigator (or designate) must complete the information in the electronic AE/ SAE form in eSource WITHIN 24 HOURS. The AE and the SAE form in eSource is the same form. When the user indicates that an AE meets the definition of 'serious', the rest of the form related to SAE information unlocks and the user is required to enter the SAE information. The report will always be completed as thoroughly as possible with all available details of the event. Even if the Investigator does not have all information regarding a SAE, the report should still be completed within 24 hours. Once additional relevant information is received, the report should be updated WITHIN 24 HOURS.

The Investigator will always provide an assessment of causality within **24** hours of submission of the SAE.

*(Amended 06 May 2015.)*

##### **9.4.4.1. Back-up system in case the electronic reporting system does not work**

If the electronic reporting system does not work, the Investigator (or designate) must complete, then date and sign a paper *AE of specific interest (clinical symptoms of thrombocytopenia)*/ SAE form and fax it to the Back-up Study Contact for Reporting SAEs within 24 hours.

This back-up system should only be used if the electronic reporting system is not working and NOT if the system is slow. As soon as the electronic reporting system is working again, the Investigator (or designate) must complete the electronic AE/ *AE of specific interest (clinical symptoms of thrombocytopenia)*/ SAE form in eSource within 24 hours. The final valid information for regulatory reporting will be the information reported through the electronic *AE of specific interest (clinical symptoms of thrombocytopenia)*/ SAE reporting system.

*(Amended 06 May 2015.)*

**9.4.5. Completion and transmission of pregnancy reports to the contracted research organisation (Quintiles)**

Once the Investigator becomes aware that a subject is pregnant, the Investigator (or designate) must complete the required information onto the electronic pregnancy form in eSource WITHIN 2 WEEKS.

Note: Conventionally, the estimated gestational age (EGA) of a pregnancy is dated from the first day of the last menstrual period (LMP) of the cycle in which a woman conceives. If the LMP is uncertain or unknown, dating of EGA and the estimated date of delivery (EDD) should be estimated by ultrasound examination and recorded in the pregnancy report.

**9.4.6. Updating of adverse events of specific interest (clinical symptoms of thrombocytopenia), serious adverse events, and pregnancy information after removal of write access to the subject's eSource (Amended 06 May 2015)**

When additional *AE of specific interest (clinical symptoms of thrombocytopenia)*, SAE, or pregnancy information is received after removal of the write access to the subject's eSource, new or updated information should be recorded on the appropriate paper report, with all changes signed and dated by the Investigator. The updated report should be faxed to the Back-up Study Contact for Reporting *AE of specific interest (clinical symptoms of thrombocytopenia)*, SAEs, and pregnancy information within the designated reporting time frames specified in [Table 21](#).

*(Amended 06 May 2015.)*

**9.4.7. Regulatory reporting requirements for serious adverse events**

The Investigator will promptly report all SAEs to the CRO (Quintiles) in accordance with the procedures detailed in [Section 9.4.1](#). The sponsor (GSK Biologicals) has a legal responsibility to promptly notify, as appropriate, both the local regulatory authority and other regulatory agencies about the safety of a product under clinical investigation. Prompt notification of SAEs by the Investigator to the Study Contact/ Back-up Study Contact for Reporting SAEs is essential so that legal obligations and ethical responsibilities towards the safety of other subjects are met.

Investigator safety reports are prepared according to the CRO's (Quintiles) policy and are forwarded to Investigators as necessary. An Investigator safety report is prepared for an SAE that is both attributable to the Investigational vaccine and unexpected. The purpose of the report is to fulfil specific regulatory and GCP requirements, regarding the product under investigation.

## **9.5. Follow-up of adverse events, serious adverse events, and pregnancies**

### **9.5.1. Follow-up of adverse events and serious adverse events**

#### **9.5.1.1. Follow-up during the study**

After the initial AE/ *AE of specific interest (clinical symptoms of thrombocytopenia)*/ SAE report, the Investigator is required to proactively follow each subject and provide additional relevant information on the subject's condition to the CRO (Quintiles) (within 24 hours for *AEs of specific interest (clinical symptoms of thrombocytopenia)* and SAEs; refer to [Table 21](#)).

All *AEs of specific interest (clinical symptoms of thrombocytopenia)* and SAEs documented at a previous visit/ contact and designated as not recovered/ not resolved or recovering/ resolving will be reviewed at subsequent visits/ contacts until the end of the study.

All AEs documented at a previous visit/ contact and designated as not recovered/ not resolved or recovering/resolving will be reviewed at subsequent visits/ contacts until 30 days after the last vaccination.

*(Amended 06 May 2015.)*

#### **9.5.1.2. Follow-up after the subject is discharged from the study**

The Investigator will follow subjects with *AEs of specific interest (clinical symptoms of thrombocytopenia)* and SAEs until the event has resolved, subsided, stabilised, disappeared, or until the event is otherwise explained, or the subject is lost to follow-up.

If the Investigator receives additional relevant information on a previously reported *AE of specific interest (clinical symptoms of thrombocytopenia)* or SAE, he/ she will provide this information to the CRO (Quintiles) using an electronic AE/ *AE of specific interest (clinical symptoms of thrombocytopenia)*/ SAE form in eSource.

The sponsor (GSK Biologicals) may request that the Investigator performs or arranges the conduct of additional clinical examinations/tests and/or evaluations to elucidate as fully as possible the nature and/or causality of the *AE of specific interest (clinical symptoms of thrombocytopenia)* or SAE. The Investigator is obliged to assist. If a subject dies during participation in the study or during a recognised follow-up period, the CRO (Quintiles) will be provided with any available post-mortem findings, including histopathology.

*(Amended 06 May 2015.)*

### **9.5.2. Follow-up of pregnancies**

Pregnant subjects will be followed to determine the outcome of the pregnancy. At the end of the pregnancy, whether full-term or premature, information on the status of the mother

and child will be forwarded to the CRO (Quintiles) using the electronic pregnancy form and the electronic AE/ SAE form, both in eSource, if applicable. Generally, the follow-up period doesn't need to be longer than 6 to 8 weeks after the estimated date of delivery.

Regardless of the reporting period for SAEs for this study, if the pregnancy outcome is a SAE, it should always be reported as SAE.

## **9.6. Treatment of adverse events**

Treatment of any AE is at the sole discretion of the Investigator and according to local standard of care. Any medication administered for the treatment of an SAE should be recorded in the subject's eSource (refer to [Section 6.7](#)).

## **9.7. Unblinding**

GSK Biologicals' policy (which incorporates ICH E2A guidance, EU Clinical Trial Directive and US Federal Regulations) is to unblind the report of any SAE which is unexpected and attributable/suspected to be attributable to the investigational vaccine, prior to regulatory reporting. The Investigator is responsible for unblinding the treatment assignment in accordance with the specified timeframes for expedited reporting of SAEs (refer to [Section 9.4.1](#)).

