### **5.3. Method of blinding**

The blinding level will change in the course of the study:

- **Observer-blind** from study start until the interim analysis that will be conducted when safety, reactogenicity and immunogenicity (including at least anti-GP EBOV data at Day 30) data is available from all subjects up to 30 days after vaccination at Day 0 (refer to [Section 11.11.1](#) for more information on this interim analysis). By observer-blind, it is meant that the vaccine recipient and those responsible for the evaluation of any study endpoint will all be unaware of which vaccine was administered. To do so, vaccine preparation and administration at Day 0 will be done by authorised medical personnel who will not participate in any of the study clinical evaluation assays.

*To ensure blinding of the site staff when preparing and administering the study vaccine details of vaccine management will be defined in a site vaccine management plan before site initiation.*

*(Amended 06 May 2015.)*

- **Single-blind** as of the interim analysis. At the time of the interim analysis, the study will become single-blind to ensure full data availability. By single-blind, it is meant that vaccination centre and sponsor personnel are aware of the treatment assignment but the subject is not.

The laboratory in charge of the laboratory testing will be blinded to the treatment, and codes will be used to link the subject and study (without any link to the treatment attributed to the subject) to each sample.

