## 6.5. Replacement of unusable vaccine doses

In addition to the vaccine doses provided for the planned number of subjects (including over-randomisation when applicable), at least 20% additional vaccine doses will be supplied to replace those that are unusable.

Staff responsible for preparing the vaccine will provide to the Investigator the next available vaccine vial for the relevant treatment as assigned by the IWRS/ IVRS in case of a replacement. Replacement vaccine vial numbers will be recorded in the IWRS/IVRS by the staff preparing the vaccine. In addition, the original unusable vaccine vial number will be reported in the IWRS/ IVRS as such.

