## **9.8. Emergency unblinding**

Unblinding of a subject's individual treatment code should occur only in the case of a medical emergency, or in the event of a serious medical condition, when knowledge of the treatment is essential for the clinical management or welfare of the subject, as judged by the Investigator.

The emergency unblinding process consists of the automated system IWRS/ IVRS that allows the Investigator to have unrestricted, immediate and direct access to the subject's individual study treatment.

The Investigator has the option of contacting the CRO's (Quintiles) Medical Expert if he/ she needs medical advice or needs the support of the CRO prior to performing the unblinding.

Any emergency unblinding must be recorded in IWRS/ IVRS and eSource by the Investigator within 24 hours.

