### 11.5.2. According-to-protocol cohort for analysis of immunogenicity

The ATP cohort for analysis of immunogenicity will include all evaluable subjects:

- Who meet all eligibility criteria.
- Who have received at least one dose of study vaccine according to protocol procedures and to their random assignment.
- For whom the randomisation code has not been broken for vaccination at Day 0.

- Who comply with the procedures and intervals defined in the protocol (refer to [Table 6](#)).
- Who did not receive a concomitant medication/ product/ vaccination leading to elimination from an ATP analysis as listed [Section 6.7.2](#).
- Who did not present with a medical condition leading to elimination from an ATP analysis as listed [Section 6.8](#).
- For whom data concerning immunogenicity endpoint measures are available.

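### Until the Day 30 interim analysis, Protocol Sections 9.7 and 6.5 give the blinded Investigator a code-break duty and a replacement-vial handover that conflict with the observer-blind

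*Protocol*

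**What the plan says.** Protocol Section 5.3 sets the standard until the interim analysis: "the vaccine recipient and those responsible for the evaluation of any study endpoint will all be unaware of which vaccine was administered". It gives Day 0 preparation and administration to "authorised medical personnel who will not participate in any of the study clinical evaluation assays". Section 5.2.2.2.1 limits unblinded treatment information in IWRS/IVRS to unblinded site staff.

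Three other rules bear on the Investigator:

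- Section 9.7 describes the sponsor's policy of unblinding reports of unexpected SAEs that are, or may be, attributable to the vaccine before they go to regulators. It then adds: "The Investigator is responsible for unblinding the treatment assignment in accordance with the specified timeframes for expedited reporting of SAEs".
- Section 9.8 states: "Unblinding of a subject's individual treatment code should occur only in the case of a medical emergency". The same sentence also allows a break for a serious medical condition, but only when knowing the treatment is essential to the subject's management or welfare.
- Section 6.5, on unusable doses, states: "Staff responsible for preparing the vaccine will provide to the Investigator the next available vaccine vial for the relevant treatment".

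Section 11.5.2 admits to the ATP immunogenicity cohort only subjects "For whom the randomisation code has not been broken for vaccination at Day 0". SAP Section 5.4 repeats this criterion. Neither document distinguishes the purpose of the break.

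**The concern.** The Investigator is an endpoint evaluator, and two protocol rules can put the allocation in that person's hands while the site is meant to be blind.

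Relatedness matters even though every analysis is descriptive. It is tabulated for AEs (Section 11.8). An SAE considered related is a holding rule and leads to an ad hoc IDMC meeting (Section 9.10). Section 9.3.3.2.2 lets the Investigator change a causality opinion as information arrives, and no rule covers a change made after the code is known. The same Investigator goes on assessing that child's later events and outcomes.

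There is a smaller consequence for immunogenicity. A reporting procedure set off by a vaccine-attributed event can remove the child from the ATP cohort.

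**Working it through.** No plan figure needs reproducing. The check sets the sections side by side.

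**1. Is the Investigator someone who must be blind?** Section 5.3 covers "those responsible for the evaluation of any study endpoint will all be unaware of which vaccine was administered". The Investigator completes Diary Cards at study visits (5.6.14.1), grades the intensity of unsolicited AEs (9.3.3.2.1) and assesses outcome (9.3.3.3). On causality, 9.3.3.2.2 says: "The Investigator is obligated to assess the relationship between the study vaccination and the occurrence of each AE/ SAE". So yes.

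**2. Can Sections 9.7 and 9.8 both be followed?** Take an unexpected, attributable SAE in a child whose care does not depend on knowing the vaccine. Section 9.7 has the Investigator break the code. Section 9.8, with its word *only*, does not permit it. A site cannot satisfy both. Section 9.4.7 places notification of authorities on the sponsor, so nothing in the documents requires the evaluator to see the code. The glossary definition of observer-blind allows personnel outside clinical evaluation to be aware of the assignment.

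**3. In what order do rating and code break occur?** The trigger in 9.7 presupposes a judgement of attribution.

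| Place | Timing of causality rating |
|---|---|
| 9.3.3.2.2 | before the SAE form is submitted |
| 9.4.4 and Table 21 footnote | within 24 hours of submission |
| 9.4.1, to which 9.7 refers | gives reporting timeframes, with no order between rating and code break |

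- Under 9.3.3.2.2, the first rating is made blind. Later revisions and later assessments of that child are not protected.
- Under 9.4.4 and Table 21, the rating may follow submission. No rule then ensures that even the first rating precedes the code break.

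**4. What does a broken code do to the analysis sets?**
- Safety is analysed on the TVC (11.8), whose definition does not depend on the code. Loss: none.
- ATP immunogenicity: read literally, 11.5.2 excludes the child. One child in a group of about 300 is 1/300 = 0.33%.
- The complementary TVC immunogenicity analysis is added at 5% exclusions in any group (11.9; SAP Section 14). With 300 children, that is 0.05 × 300 = 15.

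**5. What does Section 6.5 do?** Table 14 describes ChAd3-EBO-Z as a liquid in a vial, and Nimenrix as a powder in a vial with a prefilled diluent syringe. An unmasked vial would therefore reveal the assignment. Handing it to the Investigator contradicts the separation of roles in 5.3 and the access limit in 5.2.2.2.1. Section 6.5 does not say whether the vial is masked. Section 5.3 leaves vaccine handling to a site vaccine management plan, which was not supplied.

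**6. How long does this last?** Only until the interim analysis; after that, site personnel know the assignment by design (5.3). This can exceed 30 days for an individual child. Day 0 vaccination is staggered over three age strata with IDMC reviews between them (9.10), and the interim waits for Day 30 data from all subjects (11.11.1).

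**The case against.** The strongest reply is about sequence. The code break follows a judgement that the SAE is attributable, and 9.3.3.2.2 requires that judgement before submission. A reader might infer from 9.7 that the observer-blind fails for exactly the children whose causality rating matters most. The documents do not support this: the rating that triggers the break is normally made blind. What survives is the unprotected later revision, the later assessments, and the conflicting 24-hour wording.

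Other points for the plan:

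- *Two pathways.* Section 9.8 is headed as emergency unblinding and 9.7 covers regulatory unblinding, so they could be meant to coexist. That is a fair reading of intent, but the restriction in 9.8 is worded generally and neither section refers to the other.
- *Holding rule.* The initial rating prompts the IDMC meeting, the IDMC sees unblinded data, and nothing says that a later re-rating cancels the process. This stands and limits the consequence. The documents do not say how a re-rating after a code break is to be treated.
- *Endpoints.* The primary AE and SAE endpoints count occurrence regardless of relatedness. This stands; relatedness affects the tabulations and the safety monitoring.
- *Replacement vials.* Section 5.3 and the site plan may in practice keep vials from the Investigator or mask them. That is possible but cannot be checked. Section 3 calls adherence to the design requirements essential, so 6.5 should name the right person.

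**Conclusion.** The point holds as a conflict in the protocol that should be fixed. Sections 9.7 and 6.5 assign tasks to the Investigator that do not fit Sections 5.3, 5.2.2.2.1 and 9.8, and the timing of the causality rating is stated in two ways.

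The size is modest and cannot be given as a count. The documents give no expected number of unexpected attributable SAEs and no dose-replacement rate. A reader might take the 20% additional doses in 6.5 as a guide to how many children are affected, but that is a supply reserve and says nothing about how many receive a replacement. Nor should the two issues be merged: 6.5 concerns children whose dose was unusable, and nothing links them to children with related SAEs.

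The main safety analysis loses no one. Each code break costs the ATP immunogenicity cohort one child, about 0.3% of a group. The conclusion assumes that the ATP criterion is applied literally to any Day 0 code break. For 6.5, it also assumes that the vial is not masked under the site plan.

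**What to change.** By amendment:

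1. In 9.7, assign regulatory unblinding to CRO or sponsor safety staff who take no part in endpoint evaluation, with no disclosure to the site. Keep Investigator code breaks under 9.8, and cross-refer the two sections.
2. Reconcile 9.3.3.2.2 with 9.4.4 and Table 21 so that the Investigator's causality rating is recorded before any code break. Flag any later change as made before or after unblinding.
3. In Protocol 11.5.2 and SAP 5.4, state that a break by the safety function, not disclosed to the site, does not count as a broken code for the ATP cohort.
4. In 6.5, name the unblinded vaccine administrator, in place of the Investigator, as the recipient of the replacement vial.

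The cost is a few sentences, a matching line in the SAP, an IWRS access setting and a flag on causality changes. Unblinded vaccine staff and a CRO safety unit already exist under the protocol. No subjects, visits or samples are added.
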